7.1.4 Treatment for minor and major surgery

In the event a subject requires an unplanned minor surgery during the interventional part of the study, the treatment schedule with BAY 1093884 will not be affected. As for the treatment of bleeds (see Section 7.1.2), the subject's pre-study hemophilia treatment can be administered, as required. It may be tailored to the subject's individual response.

The appropriate treatment of minor surgery is left to the discretion of the treating physician and/or local clinical practice.

Minor surgery is defined as any surgical procedure that does not meet the definition of major (see below), and may include (but is not restricted to) dental extractions, incision and drainage of an abscess, or excisions.

Major surgery is defined as any surgical or invasive procedure (elective or emergent) in which the overall bleeding risk may be excessive, would require a general anesthetic in an individual without a bleeding disorder, penetrates or exposes a major body cavity, could result in substantial impairment of physical or physiological functions, or requires special anatomic knowledge or manipulative skill (e.g., tonsillectomy, laparotomy, thoracotomy, joint replacement).

If major surgery is required during the subject's first 24 weeks of treatment (i.e., during Part A and B), the subject will be withdrawn from the study. If major surgery is required

after the first 24 weeks, the subject may use his own hemophilia medication and prophylaxis treatment with BAY 1093884 will be interrupted. In this case, following surgery, the subject may re-enter the study and restart prophylaxis with BAY 1093884 after discussion with the sponsor.

7.2 Identity of study treatment

Code name: BAY 1093884

Manufacturer of drug product:

Bayer AG
[name]
[name]
Germany

Manufacturer of the Investigational Medicinal Product (IMP):

Fisher Clinical Services GmbH
[name]
[name]
Switzerland

Final release of the IMP – EU, International and Emerging Markets:

Bayer AG
[name]
[name]
Germany

Importation and final release (US and Canada):

Bayer HealthCare LLC, Berkeley, California (CA)
[name]
[name]
USA

Dosage form: Ready-to-use liquid for subcutaneous injection

Strength: BAY 1093884 will be provided in vials containing either 100 mg/mL or 150 mg/mL

Description: 10 mL colorless glass vials containing either 1.6 mL of BAY 1093884 at a concentration of 100 mg/mL or 1.8 mL of BAY 1093884 at a concentration of 150 mg/mL

Storage: 2°C - 8°C

Until dispensed to the subjects, the study medication will be stored in a securely locked area, accessible to authorized personnel only.

All study drugs will be labeled according to the requirements of local law and legislation. Label text will be approved according to the sponsor's agreed procedures, and a copy of the labels will be made available to the study site upon request.

For all study drugs, a system of numbering in accordance with all requirements of Good Manufacturing Practice (GMP) will be used, ensuring that each dose of study drug can be traced back to the respective bulk batch of the ingredients. Lists linking all numbering levels will be maintained by the sponsor's clinical supplies Quality Assurance (QA) group.

A complete record of batch numbers and expiry dates of all study treatment as well as the labels will be maintained in the sponsor's study file.

7.3 Treatment assignment

Enrollment will start with recruitment into Cohort 1, followed by enrollment into Cohorts 2 and 3, according to the decisions of the DMC.

An interactive web responding system (IWRS) will be used to assign at least 1 inhibitor subject and 2 PK subjects to each cohort.

7.4 Dosage and administration

The dose selections for this study are based on the results of the Phase 1 study or are extrapolated from experience with BAY 1093884 in the Phase 1 study.

Except for injections administered at study visits, subjects will self-inject the study drug by themselves in their home, or will be injected by caregivers at home or other facility near to subject's home, or by the investigator or delegate. Subjects/caregivers will receive detailed information regarding the administration of the study medication.

The potential side effects associated with subcutaneous injections and of BAY 1093884 are detailed in the core informed consent, and will be updated as needed. All subjects/caregivers are expected to review this information at the time of study enrollment. Study site personnel should review the following topics with the subjects/caregivers: subcutaneous injection practices and needle disposal, how to use and store the medication, how to respond to the potential side effects of BAY 1093884, provide instructions on when and how to contact the treatment center for questions or concerns, and how to obtain emergency medical care if required.

7.4.1 Selection of doses in the study

The study has 2 main components – a multiple dose escalation component and a dose-finding component.

A DMC will review key safety data from the first 6 subjects after 6 weeks of dosing in each cohort before recommending opening a cohort at a higher dose. Any available data from subjects continuing in the study will also be included in the DMC review.

The sponsor will provide dose recommendations based on the PK/PD model and safety evaluation, taking into consideration the criteria described in Section 7.4.1.1. The DMC will be asked to recommend next dosing cohort using the criteria specified in this section, and may review the safety data anytime during the course of the study per the criteria described in this section.

In the event that a subject is suspended from the dosing of BAY 1093884, dosing will not resume until a full review is done by DMC and the risk-benefit is deemed acceptable for that patient. During suspension of dosing, the subject will be treated with his previous hemophilia

treatment and any other event will be treated in accordance with the local standard of care. If dosing resumes following DMC review, the subject should return to the clinic for their next sequential scheduled visit to restart study drug.

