Multiple-dose escalation component: Eight (8) new distinct subjects are planned to be enrolled in each of the 3 dose cohorts. Opening of the new cohort will only enroll new subjects. An initial dose of 100 mg SC has been selected for Dose X based on safety and PK/PD data from the Phase I study. Safety data from Dose X in N=6 subjects after 1x/week SC dose for 6 weeks will be the basis for opening the cohort for Dose Y. When acceptable safety and tolerability has been achieved in the first 6 subjects after 6 weeks of dosing, the cohort for Dose Y (not to exceed 250 mg) will be opened for enrollment of 8 new subjects. The opening of cohort to Dose Z (dose not to exceed 400 mg) follows the same process and will be based on safety/tolerability data from N=6 subjects given Dose Y once weekly for 6 weeks.

The DMC will review all available safety data and the proposed dose based on PK/PD prior to opening any cohort. Safety evaluation, including stopping criteria, is described in Sections [9.6.1.7](#) and [13.1.2](#).

Dose-finding component: This portion of the study is designed to allow for identification of the appropriate dose(s) for the Phase 3 study. The dose selection for Phase 3 will be based on both the assessment of safety and evidence of efficacy based on bleeding control assessed over a 12-week period of dosing. In each cohort at dose level X, Y and Z the subjects will continue at that dose for at least 12 weeks and efficacy information from all 8 subjects at each dose level will be used for the assessment of efficacy (based on number of bleedings). Although acceptable safety and tolerability data of 6 weeks in at least 6 subjects at Dose X is required to open the next cohort – Dose Y, all 8 subjects at Dose X will remain at dose level X for at least 12 weeks to assess the efficacy. If the next dose level is open, patients in dose level X or Y will be allowed to escalate to the next dose level after 12 weeks of treatment with BAY 1093884 if specific conditions are satisfied. First, safety criteria as defined in the protocol must be met. Second, the patient must have experienced >2 bleeds during the first 12 weeks of treatment or experienced >1 bleed during any 12-week interval after the first 12 weeks of treatment at a particular dose level. The safety criteria to be assessed for this portion of the study (individual dose escalation after 12 weeks of dosing in that particular dose cohort) are provided later in this section.

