Eight (8) new distinct subjects are planned to be enrolled in each of the 3 dose cohorts. Opening of the new cohort will only enroll new subjects. These subjects will be treated prophylactically with the X Y or Z dose of BAY 1093884 once weekly for 12 weeks (part A). At least 1 inhibitor subject (any titer) and 2 PK subjects (willing to undergo full PK evaluations) will be enrolled in each cohort.

All subjects of each cohort will continue on the dose assigned for Part A (12 weeks) to obtain safety data and individual efficacy data.

Individual subject dose escalation criteria in the dose finding part of the study:

In this portion of the study, the objective is to identify the appropriate dose(s) for the Phase 3 study. The dose selection for Phase 3 will be based on both the assessment of safety and evidence of efficacy based on individual bleeding control assessed over a 12-week period of dosing for each patient.

Subjects will be evaluated for the number of bleeds occurring during each part of the study. In particular, only the bleeds recorded as “spontaneous” (not related to any trauma or activity) and requiring additional treatment will be considered for the dose escalation efficacy evaluation, and are defined below as “bleeds.”

Evaluation at the end of Part A:

Subjects who present ≤ 2 bleeds during Part A will start Part B and continue on the same weekly dose; otherwise (if presenting >2 bleeds) subjects will escalate to the next higher opened dose cohort.

Evaluation at the end of every 12-week period of Part B and extension:

Subjects who present ≤ 1 bleed in 12 weeks, during Part B, or during the extension part, will continue on the same weekly dose; otherwise (if presenting >1 bleed) subjects will escalate to the next higher opened dose cohort.

Since dose Z is the highest dose, any subject on dose Z who meets the escalation criteria described above may withdraw from the study or may continue treatment to provide further safety and efficacy data. The decision on treatment continuation is at the subject’s and investigator’s discretion.

The first injection of any new or escalated dose will be given under medical supervision

If a subject qualifies for dose escalation based on the number of bleeds, but the next higher dose cohort has not been opened, the subject must stay on the current dose and then escalate to the next higher dose only after it is opened.

Dose selection for cohorts:

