Results from studies on hemophilia animal models support the development of clinical studies with repeated administration of BAY 1093884 in subjects with hemophilia A or B with or without inhibitors.

Results from the Phase 1 study support that subjects with FVIII or FIX deficiency and inhibitor subjects exhibit similar response to BAY 1093884 with regard to both PK and pharmacodynamics (PD) profile.

Considering the results from these studies, the dose for Cohort 1 (X dose) will be 100 mg, for Cohort 2 (Y dose) will not exceed 250 mg and the dose for Cohort 3 (Z dose) will not exceed 400 mg. Doses for Cohort 2 and 3 (Y and Z doses) will be selected based on the safety assessments from previous cohorts, PK/PD model and the criteria described in detail in Section 7.4.1.1, together with the criteria for evaluating safety rules.

Throughout the study, the safety rules for an occurrence of a single drug-related SAE (SAR) related to study drug, or two severe or clinically significant AEs considered to be at least possibly related to study drug will be followed. In the event that a subject is suspended from the dosing of BAY 1093884, dosing will not resume until a full review is done by DMC and the risk-benefit is deemed acceptable for that patient. During suspension of dosing, the subject will be treated with his previous hemophilia treatment and any other event will be

treated in accordance with the local standard of care. If dosing resumes following DMC review, the subject should return to the clinic for their next sequential scheduled visit to restart study drug.

Data Monitoring Committee

A DMC will regularly review key safety data and give recommendations on:

- Dose escalation (opening the next dose cohort);
- Opening of the Extension Part

In addition, the DMC will meet on an *ad hoc* basis as appropriate to ensure subject safety oversight in the trial.

The DMC may recommend modifying or stopping the study early due to safety concerns at any time, based on these periodic and *ad hoc* data reviews.

The full description of DMC review is provided in Sections 9.6.1.7 and 13.1.2, and in the DMC charter.

Justification of study design

At the highest dose investigated in the Phase 1 study, complete inhibition of TFPI (defined as TFPI levels below the lower limit of quantification of the assay and corresponding to at least 82-87% of inhibition) was observed in all subjects for at least 7 days.

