A DMC will review key safety data and dose recommendation before recommending escalation to the next dosing cohort.

At a minimum, safety/PK/PD data from 6 subjects completing 6 weeks in Cohort 1 (Dose X) are needed to open Cohort 2 (Dose Y). All available safety information will be taken into consideration. This may include data from the 2 additional subjects in the cohort who may

not have reached the 6 weeks or additional data from any of the first 6 subjects who may have been dosed for longer than 6 weeks. This guideline will apply to further cohorts as well. All available safety information from ongoing subjects will be used for safety evaluation in opening the next dose cohort. This includes safety data also from the subjects who may have escalated from a previous cohort. Details on the criteria for dose escalation can be found in the DMC charter.

Any subject from dose cohort X can escalate to the dose level Y only after dose Y has been opened (i.e., after data from 6 subjects is available after 6 weeks of treatment), the subject in dose cohort X has been treated for at least 12 weeks and meets the individual dose escalation criteria described in the study design section. Equally, any subject from dose cohort Y can escalate to the dose level Z only after dose Z has been opened and the subject in dose cohort Y has been treated for at least 12 weeks at dose level Y.

The current PK/PD model will be updated with data from a minimum of 6 subjects dosed for 6 weeks in each cohort and will include any additional data from all ongoing subjects prior to decision for opening a cohort. This updated model will be used to propose the next dose level for the new cohort.

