9.2.1.7 Phone call (3 weeks \pm 2 days after Visit 5)

The following procedures will be performed and data recorded:

- Concomitant medications
- Adverse events (see Section 9.6.1)
- Review of EPD data
- Plan next visit on day of scheduled injection with BAY 1093884. Reminder to subject to come next visit without having injected yet.

9.2.1.8 Visit 6 (12 weeks \pm 1 day after Visit 2) assessment of dose escalation

The subject's eligibility for dose escalation will be assessed at this visit. Therefore, subjects need to come to the site prior to the scheduled BAY 1093884 injection.

The following procedures will be performed and data recorded 12 weeks \pm 1 day after Visit 2:

- Concomitant medications
- Adverse events (see Section 9.6.1)
- Review of EPD data
- Local 12-lead ECG
- Body weight
- Decision if subject will stay on the current dose or if escalation is required (does not apply for subjects in Cohort 3 on Z dose; refer to Section 7.1.1 for dose escalation criteria)
- Procedures before administration of study drug
 - Physical examination (see Section 9.6.3.2)
 - Vital signs (see Section 9.6.3.3)
 - Blood samples for laboratory tests (see Sections 9.6.3.1 and 9.5.2):
 - Complete blood count (CBC), platelets, serum chemistry
 - Antibody against aTFPI (aTFPI-Ab)
 - Blood sampling for PD and exploratory biomarkers
 - PK sampling
- Administration of study drug
 - If the subject meets dose-escalation criteria, and the DMC has approved the next higher dose, the subject will receive the next higher dose under medical supervision.
 - If the subject does not meet dose-escalation criteria, or the DMC has not approved the next higher dose, the subject will receive their current dose, does not necessarily need to be injected under medical supervision.
- Procedures 30-60 minutes after administration of study drug (in case of dose escalation):
 - Vital signs (see Section 9.6.3.3)
- Return of all used and unused study medication since the last visit
- Dispensation of new study medication for next 12 weeks
- In case of dose maintenance:
 - Start documented regular contact with the subject every 4 weeks to discuss adverse events, concomitant medication, EPD review and number of untreated bleeds.
 - Plan next visit on day of scheduled injection with BAY 1093884. Reminder to subject to come next visit without having injected yet.

- In case of dose escalation:
 - Schedule additional safety visits 1 week (± 1 day) and 6 weeks (± 1 day) after dose escalation

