9.2.1.10 Every 12 weeks visit (± 7 days calculated from Visit 2)

The subject's eligibility for dose escalation will be assessed at this visit. Therefore, subjects need to come to the site prior to the scheduled BAY 1093884 injection.

Visit windows of ± 7 days (calculated from Visit 2) are allowed, but the next scheduled BAY 1093884 injection must be kept in mind to ensure subjects will not have more than 8 days in between 2 injections of BAY 1093884.

The same procedures as at Visit 6 will be performed and data recorded. Please refer to Section 9.2.1.8. Please note difference in time window compared with Visit 6.

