9.6.1.6 Dose-limiting toxicities

Dose-limiting toxicities (DLTs) are defined as any of the following events that are clearly unrelated to underlying disease and occurring at any dose level.

- Presence of any symptoms or signs of TE or TMA
- Platelets <100 giga/L or fibrinogen <100 mg/dL at any visit
- Any grade ≥ 3 according to CTCAE criteria version 5.0 (CTCAE criteria do not apply for toxicities related to underlying disease like aPTT)
- Grade ≥ 2 toxicities according to CTCAE criteria in case of symptoms of disseminated intravascular coagulation (DIC) or hemolysis

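### Suspended time on the subject's own treatment is counted in the annualized bleed rate for the BAY 1093884 dose, and after Part A the bleeds in it can meet the escalation limit

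*Protocol*

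**What the plan says.** **Suspension and restart.** Protocol 9.6.1.7 suspends dosing in a subject after one drug-related SAE, two severe or clinically significant drug-related AEs, or a dose-limiting toxicity (DLT). Section 9.6.1.6 defines DLTs as "any of the following events that are clearly unrelated to underlying disease and occurring at any dose level". The list includes any CTCAE grade 3 or higher event and does not require drug-relatedness. Section 5 adds: "During suspension of dosing, the subject will be treated with his previous hemophilia treatment". If the DMC clears him, Section 7.4.1 applies: "If dosing resumes following DMC review, the subject should return to the clinic for their next sequential scheduled visit to restart study drug". Section 7.1.4 separately interrupts dosing for major surgery after Week 24.

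**Visits and escalation.** In Table 9-1 the scheduled visits after Part A are 12 weeks apart and each is a dose decision. The only visits between them are the safety visits 1 and 6 weeks after an escalation. Section 9.2.1.10 says that the subject's "eligibility for dose escalation will be assessed at this visit". Section 5 sets the count: "Subjects will be evaluated for the number of bleeds occurring during each part of the study". Only treated spontaneous bleeds qualify, and the limits are >2 in Part A and >1 in each later 12-week period. Section 9.2.1.8 gives the consequence: "If the subject meets dose-escalation criteria, and the DMC has approved the next higher dose, the subject will receive the next higher dose"; otherwise he receives his current dose. There are two guards. Section 5 states: "First, safety criteria as defined in the protocol must be met". Section 7.4.1.1 requires that "the subject in dose cohort X has been treated for at least 12 weeks and meets the individual dose escalation criteria", with a parallel 12-week condition at dose Y.

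**Analysis.** SAP 4.5.2 runs the Part A and Part B rate windows from visit injection to visit injection. The window for the dose initially received runs from the first injection to the first escalated one. For subjects who discontinue, or who never escalate in the last case, the window ends at the later of last visit and last dose. On treatment timing, SAP 4.5 drops only bleeds before the first dose. The post-hoc plan's whole-study scope runs from first intake to study-drug intake, read here as the last. SAP 6.2 visibly removes only escalated subjects from the Part B responder periods, and the per protocol set states no minimum dosing.

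**The concern.** The protocol foresees that some subjects will spend part of a 12-week period on factor or bypassing agent instead of BAY 1093884. The visible analysis and escalation rules make no allowance for this. A subject back on his own prophylaxis can make a dose look effective. A subject back on on-demand treatment can make it look ineffective.

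According to Protocol Section 5, bleeding control over 12 weeks informs the Phase 3 dose. With 8 subjects per cohort, one subject is 1/8 = 12.5 percentage points. The escalation rule also sets the dose that an individual receives. After Part A, a subject returning from a safety suspension could meet the bleed limit for a higher dose on bleeds that occurred while he was not on the drug.

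**Working it through.** The documents give no figure to reproduce on this point and no suspension frequency. The numbers below are conditional illustrations.

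**1. Annualized rate, SAP 4.5.2.** Rate = bleeds × 365.25 / days, with the SAP 6.2.1 window read in days. A 12-week period is 84 days.

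| Assumed course in one period | Rate as written | Rate on drug only |
|---|---|---|
| 1 bleed in 14 days on drug, 0 in 70 days off | 1 × 365.25/84 = 4.3 | 1 × 365.25/14 = 26.1 |
| 2 bleeds in 42 days on drug, 0 in 42 days off | 2 × 365.25/84 = 8.7 | 2 × 365.25/42 = 17.4 |
| 0 bleeds in 42 days on drug, 2 in 42 days off | 2 × 365.25/84 = 8.7 | 0 |

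The first row fits Part B best. In Part A, with visits at Weeks 3, 6 and 12, a 10-week gap needs the DMC review to run past Week 6. If a suspension spans a boundary visit, there is no injection at that visit and the window edge is undefined.

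**2. Post-hoc whole-study scope** (adds 1 day). Take 3 bleeds in 14 weeks on drug and none in 10 weeks off.
- Restart at Week 24, with that dose closing the scope: 3 × 365.25/169 = 6.5, against 3 × 365.25/98 = 11.2 on drug.
- No restart, last injection on day 91: 3 × 365.25/92 = 11.9. The gap drops out, so this scope is affected only when dosing later resumes.

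**3. Escalation limit at restart.** Assume that treated spontaneous bleeds off drug are Poisson with mean μ = rate × 7 × weeks/365.25. Then P(>1) = 1 − e^(−μ)(1 + μ). The documents give only an entry floor of 4 bleeds in 6 months, about 8 per year, of any type and treated or not. The range used is therefore 4, 8 and 16 per year.

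| Weeks off drug | 4/year | 8/year | 16/year |
|---|---|---|---|
| 2 | 1% | 4% | 13% |
| 4 | 4% | 13% | 35% |
| 6 | 8% | 23% | 55% |
| 12 (worst case) | 23% | 55% | 88% |

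For example, at 8 per year and 4 weeks, μ = 8 × 28/365.25 = 0.613 and P(>1) = 0.126. These are probabilities of meeting the bleed limit from off-drug time alone, not of being escalated. Because restart waits for the next scheduled visit, a Part B gap can be long even when clearance is quick.

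**4. Who can be affected.** A Part A subject is stopped by the 12-week condition in 7.4.1.1, and a dose Z subject cannot escalate. That leaves dose X or Y subjects after Part A who have at least 12 weeks at their dose and whose next dose is open.

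**5. Responders.** SAP 6.2 has three responder variables. The zero-bleed item and the Part A ≤2 item refer to treatment on top of BAY 1093884, which can be read as leaving out bleeds while the drug is suspended. The Part B ≤1 item lacks that phrase. If own prophylaxis gives 3, 5 or 8 treated spontaneous bleeds per year (assumed), P(≤1 in 12 weeks off drug) is 85%, 68% or 45%. With one such subject in a cohort of 8, and exact 90% intervals:
- scored as response: 6/8 = 75% (40–95%)
- counted as non-response: 5/8 = 63% (29–89%)
- non-evaluable: 5/7 = 71% (34–95%)

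**The case against.** The strongest reply has five parts.

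- **The restart dose is not really missing.** Subjects stay on the assigned dose in Part A, and later visits give the current dose unless escalation criteria are met. No dose reduction is listed among the AE actions. This stands: the general rules imply the current dose, and the remaining gap is that escalation is not ruled out at restart.
- **Escalation after a suspension needs a chain of conditions.** DMC clearance, an opened higher dose, 12 weeks treated and the Section 5 safety criteria must all be in place, and 7.4.1.1 refers to a DMC charter that was not supplied. This stands as a limit on likelihood. It does not change the count, because no visible text discounts off-drug bleeds.
- **Responder counts have some protection.** Besides the wording in two of the three items, SAP 4.1 speaks of periods of treatment, and SAP 5.1 leaves set assignment to data review. This stands in part. No visible criterion excludes a largely off-drug Part B period, and deciding case by case in an open-label study is weaker than a pre-set rule.
- **Excluding interrupted periods from the main responder analysis would condition on a post-baseline event**, the kind of restriction SAP 6.2 itself warns about. This stands, and the fix leaves that analysis as planned.
- **Little depends on it.** Safety is primary, there are no hypothesis tests, the annualized rate is an additional analysis that the SAP calls imprecise, individual data are listed, and Phase 1 reported no SAEs in 32 subjects. This lowers the weight but does not justify a rate credited to the wrong treatment when the correction is simple.

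**Conclusion.** The point holds most firmly for the annualized bleed rate. As written, SAP 4.5.2 credits suspended and surgically interrupted time, and the bleeds in it, to the dose. In the examples this moves a subject's rate from 26.1 to 4.3 per year, or from 0 to 8.7. The post-hoc whole-study scope shares the problem only when the subject later restarts.

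The escalation part holds narrowly, for dose X or Y subjects after Part A whose next dose is open. The responder part holds for the Part B ≤1 item. The responder intervals in the example overlap widely.

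A reader might infer that the protocol leaves the restart dose entirely open, that suspended subjects will be escalated after a safety event, or that all three responder counts are affected. The documents do not support these readings. The dose rules imply the current dose, the safety criteria and DMC clearance may block escalation, and two responder definitions may already exclude off-drug bleeds.

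The size depends on assumed bleed rates and gap lengths. Suspensions may be rare, although a DLT need not be drug-related to trigger one. Redacted text and the DMC charter could not be checked. This is worth correcting but is not a threat to the primary safety objective.

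**What to change.** **SAP 4.5.2 and the post-hoc scopes.** Remove suspended or surgically interrupted time, and the bleeds in it, from the annualized rate. Say how a window is closed when no injection is given at a boundary visit.

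**Protocol Sections 5, 7.4.1 and 9.2.1.8.** State that the subject restarts at the dose held before suspension, that bleeds during suspension do not count toward the >2 or >1 limits, and that no escalation occurs at the restart visit. The next decision follows 12 weeks of actual dosing.

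**SAP 6.2.** Keep the planned responder analysis. Add a sensitivity display in which any 12-week period with 2 or more consecutive missed weekly doses is shown once as non-evaluable and once as non-response.

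**Cost.** A few protocol sentences and a short SAP rule. No new data are needed, because diary injection dates (9.4.1) and the AE action for interrupted drug (9.6.1.2.4) help to identify the gaps. The downside is slightly less exposure time in the rate and an occasional delayed escalation.
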